#### **10.4 Clinical Laboratory Data**

Hematology, clinical chemistry, and urine analysis laboratory assessments, not discussed below in [Section 10.4.1](#), collected at each study visit and the changes from baseline to any post-baseline visit will be summarized by descriptive statistics. All laboratory tests will be compared to their laboratory normal range. Values outside of the normal range will be further classified as: Low – CS, High – CS, Low – NCS, High – NCS. Additionally, a shift table will be created to present any change from baseline in normal ranges in all laboratory tests across all post-baseline visits. This table will show the number and percentage of patients who had values that shifted from low - CS, low-NCS, normal, high – NCS, or high-CS at baseline to low - CS, low-NCS, normal, high – NCS, or high-CS at each post-baseline visit. Percentage of patients will be calculated using the number of patients with a baseline value and a non-missing value at the specified post-baseline visit as the denominator.

All laboratory data will be presented in data listings as collected. The listings will show the sample date, laboratory test, indicator test was not done (if applicable), reason test was not done (if applicable), laboratory value, and the change from baseline. Values outside of the reference range will be flagged with ‘H’ for high and ‘L’ for low, respectively.

## 10.5 Vital Signs

The aggregated vital signs (described in [Section 3.5.1](#) and [3.5.2](#)) at each study visit and the changes from baseline to any post-baseline visit will be summarized using descriptive statistics.

Vital signs will be presented in a listing. The listing will show the assessment date, vital sign, indicator measurement was not done (if applicable), measurement value, and the change from baseline. Values will include both the triplicate measurements and their aggregated value, where applicable.

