12 Safety laboratory tests will include CBC with platelet count and standard indices, chemistry panel (includes sodium, potassium, chloride, CO2, albumin, total protein, glucose, BUN, creatinine, uric acid, aspartate aminotransferase (AST), alanine aminotransferase (ALT), gamma-glutamyl transferase (GGT), creatine phosphokinase (CPK), alkaline phosphatase, total bilirubin, direct bilirubin, lactate dehydrogenase (LDH), calcium, phosphorus), thyroid- stimulating hormone (TSH) and urinalysis with microscopic analysis if positive findings on dipsticks warrant further examination. Due to the age of the children, it may not be possible to collect samples (including urine samples) for all laboratory tests at every study visit. Screening may be performed over multiple days, to complete the required assessments. After enrollment, if all laboratory tests are not possible, then the tests should be collected in the following descending order of priority: safety, anti-drug antibodies, [REDACTED], [REDACTED] and then [REDACTED]. If it is not possible to collect the safety laboratory tests on two consecutive visits, the patient should be discussed with the Sponsor. If there is a marginal value close to the exclusion range, it is suggested to repeat the laboratory analyses at Investigator's discretion. To allow for pre- and post-dose sampling, patients will attend the site visit having fasted for an 8-hour time period without injecting the trial product. On the day of the site visit, dosing will be conducted on site. The Investigator's will adhere to the site-specific blood volume limits for safety laboratory and [REDACTED] to ensure minimal distress to the pediatric patients. If the genetic sample cannot be collected at the enrollment visit, it may be collected during a later trial visit. Anti-drug antibody samples (Section 8.5) are to be collected prior to dosing with setmelanotide. [REDACTED]

13 [REDACTED]

14 [REDACTED]

15 [REDACTED]

16 [REDACTED]

17 [REDACTED]

-  Bone age may be read locally initially, but the Sponsor may request central reading of images. A standard bone age measurement (of the hand/wrist area) will be obtained at the beginning and the end of the trial to monitor for growth related safety concerns.

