#### 5.1.3. Enrollment and trial procedures

At the enrollment visit, patients will undergo all procedures as outlined in the SoA ([Table 1](#)) and it will be reconfirmed that the patient continues to meet all of the Inclusion and none of the Exclusion criteria of the trial.

At the enrollment visit, the patient will have height and body weight recorded. This will be the baseline height and weight. To be eligible for the trial, a patient's baseline weight must be at least 15 kg. Height and weight will be monitored closely during the trial.

During the enrollment visit, the caregiver will administer the patient's first dose of setmelanotide via subcutaneous (SC) injection under the supervision of the trial staff. Patients' caregivers will be issued an electronic diary to capture daily compliance with injections.

All patients will begin treatment with setmelanotide at a dose of 0.5 mg per day. Patients will then increase their dose by 0.5 mg increments, every 2 weeks, as described in the SoA ([Table 1](#)). The maximum dose level of setmelanotide used in this trial will be based on the weight bands for the 2- to <6-year-old patients to support an exposure similar to that observed for adults dosed at 2 to 3 mg setmelanotide QD. The maximum dose level in this trial for patients who weigh [REDACTED] will be 0.5 mg, 1.0 mg, 1.5 mg and 2.0 mg QD, respectively.

If a patient's weight decreases to below 15 kg during the trial, the Investigator and Rhythm Pharmaceuticals, Inc. (henceforth Sponsor) will discuss the patient's status and will jointly

determine if a patient should continue the current dose, decrease the dose or discontinue treatment with setmelanotide temporarily or permanently. A dose reduction to 0.25 mg QD can be considered in such scenarios or in case of tolerability concerns, including for example, the occurrence of severe renal impairment. These dose adjustments are considered adequate for the pediatric patients to grow in height at a normal rate and support attaining and maintaining an appropriate body weight.

At the discretion of the Investigator, the dose escalation for a patient may be temporarily paused at any step prior to reaching their final maintenance dose, for safety or tolerability reasons, or due to achieving adequate weight loss. The dose may continue to be evaluated and adjusted, at the discretion of the Investigator, so long as the daily dose is kept between 0.25 mg and 2.0 mg QD, according to their respective weight.

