### 3.3 Treatments and Assignment to Treatments

All patients will begin treatment at a dose of 0.5 mg of setmelanotide per day administered as a SC injection. Patients will then increase their dose by 0.5 mg increments, every 2 weeks, as described in the SoA ([Section 16.1](#)). The maximum dose level of setmelanotide used in this study will be based on the weight bands for the 2- to <6-year-old patients to support an exposure similar to that observed for adults dosed at 2 to 3 mg setmelanotide QD. The maximum dose level in this study for patients who weigh [REDACTED] will be 0.5 mg, 1.0 mg, 1.5 mg and 2.0 mg QD, respectively.

If a patient's weight decreases to below 15 kg during the study, the Investigator and Sponsor will discuss the patient's status and will jointly determine if a patient should continue the current dose, decrease the dose or discontinue treatment with setmelanotide temporarily or permanently.

A dose reduction to 0.25 mg can be considered in such scenarios or in case of safety or tolerability concerns, including for example, the occurrence of severe renal impairment. These dose adjustments are considered adequate for the pediatric patients to grow in height at a normal rate and support attaining and maintaining an appropriate body weight.

At the discretion of the Investigator, a patient may temporarily pause the dose escalation at any step prior to reaching their final maintenance dose, for safety or tolerability reasons, or due to achieving adequate weight loss. The dose may continue to be evaluated and adjusted, at the discretion of the Investigator, so long as the daily dose is kept between [REDACTED] and 2.0 mg QD, according to their respective weight.

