### 3.5 Patient Assessments

#### 3.5.1 Vital Signs

Vitals signs include:

- Height (cm)
- Weight (kg)
- [REDACTED]
- Temperature (C)
- Heart Rate (HR) (beats/min)
- Systolic Blood Pressure (mmHg)
- Diastolic Blood Pressure (mmHg)
- Respiratory Rate

Vital signs will be assessed from screening and at every post-baseline visit. Height, weight, HR, systolic blood pressure, and diastolic blood pressure will be measured in triplicates at each visit. In addition to the individual measurements the above items will be aggregated into a mean value per visit (i.e. mean of all height measurements).

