### 4.3 Baseline Definitions

For all analyses, baseline will be defined as the most recent measurement prior to the first administration of study drug, including assessments done at the Screening visit, Unscheduled visits conducted prior to study treatment, and pre-treatment assessments done at the Enrollment (Baseline) visit.

In general, change from baseline ( $\Delta$ ) will be calculated as the value at a given time point,  $X$ , minus the baseline value:

$$\Delta = X \text{ Value} - \text{Baseline Value}$$

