## 8 Demographic and Baseline Characteristics

### 8.1 Demographic and Baseline Characteristics

Demographic assessments for this study include:

- Age (years)
- Gender
- Ethnicity
- Race
- Weight at Baseline (kg)
- Height at Baseline (cm)
- Body Mass Index (BMI) at Baseline ( $\text{kg/m}^2$ )
- BMI Z-score at Baseline
- Waist Circumference at Baseline (cm)
- Gene Type (*POMC*, *PCSK1*, *LEPR*, and BBS)
- Fitzpatrick Skin Type (FST) at Baseline

Age, baseline weight, baseline height, baseline BMI, baseline BMI Z-score, and baseline waist circumference will be analyzed as a continuous variable. Gender, ethnicity, race, gene type, and baseline FST will be analyzed as categorical variables.

Demographics characteristics will be presented by patient in a data listing.

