### 9.1 Primary Efficacy Endpoints

#### 9.1.1 Proportion of Patients with a Decrease from Baseline to 52 Weeks in BMI Z-score $\geq 0.2$

A “responder” is defined as a decrease from baseline to 52 weeks in the patient’s BMI z-score of  $\geq 0.2$ . The WHO Child Growth Standards 2007 will be used for BMI z-score. At each visit, an indicator variable will be created to identify patients that have a decrease in BMI z-score from baseline of 0.2 or more, allowing for the analysis of proportion of patients who meet the “responder” definition. The proportion and the corresponding 2-sided 95% CI using the Clopper-Pearson method will be reported for each visit. Sample SAS code to calculate the BMI z-score can be found at <https://www.who.int/tools/child-growth-standards/software>.

#### 9.1.2 Mean Percent Change in BMI from Baseline to Week 52

For the analysis of Mean percent change in BMI from baseline, percent changes in BMI from baseline over time will be summarized using descriptive statistics. Mean percent change in BMI from baseline over time will also be provided graphically. A 2-sided 95% CI with Student’s *t*-distribution will be provided for Mean percent change in BMI from baseline. In addition, patient figures showing the percent change in BMI from baseline will be created. Information on the patient’s baseline BMI will be included in the figure.

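### Height is summarised only in centimetres, so the planned summaries cannot show whether children grew normally on treatment

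*SAP*

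**What the plan says.** **Measurement.** SAP 3.5.1 lists height, in cm, among the vital signs: "Height, weight, HR, systolic blood pressure, and diastolic blood pressure will be measured in triplicates at each visit". The readings are averaged to one value per visit.

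**Analysis.** SAP 10.5 states that the aggregated vital signs "at each study visit and the changes from baseline to any post-baseline visit will be summarized using descriptive statistics". It adds a per-patient listing of the triplicates, their mean and the change from baseline. Under SAP 4.3, change "will be calculated as the value at a given time point" less the baseline value. SAP 8.1 reports baseline height in cm only, whereas BMI appears both as a raw value and as a z-score.

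**Growth as a stated consideration.** Protocol 5.1.3 says of its dose adjustments: "These dose adjustments are considered adequate for the pediatric patients to grow in height at a normal rate". SAP 3.3 gives the same rationale. A footnote to Protocol Table 1 says that a hand/wrist bone age "will be obtained at the beginning and the end of the trial to monitor for growth related safety concerns".

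**A growth reference already in use.** SAP 9.1.1 states: "The WHO Child Growth Standards 2007 will be used for BMI z-score".

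**Other growth data.** Protocol 8.1.2 asks for growth charts since birth. SAP 8.2 lists the 10 most recent historic heights with dates. SAP 10.8 summarises bone age and its change from baseline to end of treatment. Protocol 7.6 confirms a single open-label arm.

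**The concern.** A change from baseline in centimetres can be read as a safety result only if the reader knows what change to expect. For blood pressure or heart rate, no change is a reasonable first benchmark. For height in this age group it is not: every child is expected to gain, and the expected gain depends on age and sex. A positive mean change is therefore compatible with normal growth and with markedly slowed growth. With about 10 to 15 children spread over four years of age, the mean also depends on the age mix. With no control arm and no reference value, nothing in the planned table separates these cases.

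Growth is an obvious safety question for a weight-reducing drug in young children, and the plan itself invokes normal height growth when it explains its dose adjustments. Height is also the denominator of BMI, so a reader who wants to interpret a BMI change needs to know what height did.

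**Working it through.** The plan states no figure on this point, so there is none to reproduce. The check asks what the planned summary would show if growth had slowed.

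**Inputs from the documents**
- Height in cm, mean of triplicates: SAP 3.5.1.
- Change = visit value − baseline value: SAP 4.3.
- Summary of value and change, descriptive only: SAP 10.5.
- One arm, about 10 to 15 patients: Protocol 7.6, SAP 3.4.

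**Assumed inputs (not in the documents)**
- Normal gain *g* = 5 to 9 cm over one year.
- SD of height for age = 4 to 5 cm.
- Fractional slowing *s* = 0.5 in the main illustration.

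**Formulas**
- Observed change = *g* × (1 − *s*)
- Shortfall = *g* × *s*
- Approximate fall in height z-score = *g* × *s* / SD

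**Results at half-normal growth**

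| *g* (cm/year) | Change shown | Shortfall | z fall, SD 5 cm | z fall, SD 4 cm |
|---|---|---|---|---|
| 5 | +2.5 cm | 2.5 cm | 2.5/5 = 0.50 | 2.5/4 = 0.63 |
| 9 | +4.5 cm | 4.5 cm | 4.5/5 = 0.90 | 4.5/4 = 1.13 |

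The planned summary shows a gain of 2.5 to 4.5 cm, while the standardised score falls by about 0.5 to 1.1. The upper end pairs the fastest assumed growth with the smallest assumed SD.

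**Other degrees of slowing, with *g* = 5 to 8 cm/year and SD 4 to 5 cm**
- 25%: +3.75 to +6.0 cm shown; z fall about 0.25 to 0.5.
- 75%: +1.25 to +2.0 cm shown; z fall about 0.75 to 1.5.

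The displayed change is positive in every scenario.

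**Would the spread of the data give a warning?** Take *g* = 6 and *s* = 0.5, so the mean change is +3.0 cm, and assume an SD of change of 2 cm. The 95% half-width is t × SD/√n:
- n = 10: 2.262 × 2/√10 = 1.43, interval 1.57 to 4.43 cm.
- n = 15: 2.145 × 2/√15 = 1.11, interval 1.89 to 4.11 cm.

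The SAP does not plan this interval for height. It is shown only to make clear that even at halved growth the result would sit well above zero.

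**Direction of any effect on the primary endpoints.** BMI = weight/height². At a given weight, a smaller height gain gives a larger BMI. That works against both a BMI z-score decrease of at least 0.2 and a percent decrease in BMI.

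**The case against.** The strongest reply is that the data are all there. SAP 10.5 lists every height for every child. SAP 8.2 lists up to 10 dated historic heights, and Protocol 8.1.2 calls for growth charts since birth. With about 10 to 15 patients, someone could compare growth before and during treatment child by child. Bone age is a named secondary endpoint, taken expressly for growth-related safety. This much stands. A reader might infer that slowed growth would go unnoticed; the documents do not support that. What they support is narrower: the planned summaries would not show it. Bone age does not close that gap, because it is taken only at baseline and end of treatment, does not measure height, and has no stated comparison with chronological age in SAP 10.8.

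Second, the statement about normal height growth explains why certain dose adjustments are thought adequate. It is not an objective or endpoint. That also stands: the SAP has not left out a promised endpoint. It remains odd that the plan relies on normal growth and reports height in a form that cannot show it.

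Third, parts of the SAP are redacted, including contents entries after 9.2.4 and after 10.4, an item in 3.5.1 and the opening of section 4. A height score there cannot be excluded. It is unlikely, because the readable baseline list (8.1), efficacy variables (9) and safety endpoints (10.1) contain none.

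Finally, without a control arm a fall in height z-score could not by itself be attributed to the drug. That is true, but it is no reason to prefer a summary in which the fall cannot be seen.

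**Conclusion.** The point holds as a gap in presentation, not in data collection. In the readable SAP, height is reported as cm and change in cm, without an age and sex reference, a velocity or a comparator, so the planned tables cannot tell normal growth from slowed growth. The size given (+2.5 to +4.5 cm displayed against a z-score fall of about 0.5 to 1.1 at half-normal growth) rests wholly on assumed growth rates, height SD and degree of slowing. The qualitative result does not depend on the exact values: any slowing short of complete arrest still gives a positive change.

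A reader might also infer that impaired growth could produce a spurious response on the primary endpoints. The arithmetic points the other way: at a given weight, slower height growth raises BMI, so it would understate the primary effects rather than inflate them. The primary analysis is not invalidated.

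**What to change.** 1. In SAP 10.5, add height-for-age z-score and its change from baseline, summarised by visit. Use an age- and sex-based growth reference consistent with the one used for BMI z-score. State that it covers the full age range on study: a child just under 6 at consent, with up to 8 weeks of screening and 52 weeks of treatment (60 weeks, about 1.15 years), can be just over 7 at Week 52.
2. In SAP 8.1, add baseline height z-score beside baseline height.
3. List each patient's height z-scores over time. If the sponsor wants to flag falls beyond some size, that threshold is a display choice to be stated in the SAP, not a clinical rule.
4. Compute age from date of birth and the actual measurement date, and use measured heights only. SAP 9 carries the last height forward when height is missing for BMI; a carried-forward height at an older age would lower the z-score artificially.

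Cost: a free improvement. Triplicate heights, date of birth and gender are already collected, so the change is derived variables and output programming, with no new measurement or visit.

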## 10.6 Electrocardiograms

The ECG and the changes from pre-dose baseline will be summarized descriptively at each visit. In addition, a shift table will be created to show any change from pre-dose baseline to each visit in the overall ECG interpretation.

QTcF interval prolongation will be presented separately as well. The number and percentage of patients with a QTcF interval of >450 msec, >480 msec, and >500 msec will be summarized by visit, along with the number and percentage of patients with a change from pre-dose baseline in QTcF interval of 30 - < 60 msec and  $\geq 60$  msec.

All ECG results will be presented in a data listing. The listing will show the assessment date, ECG measurement, indicator ECG was not done (if applicable), reason ECG was not done (if applicable) ECG value, the change from baseline.

## 10.7 Hyperpigmentation

Skin examination results (described in Section 3.5.4) at each visit will be summarized by skin region using descriptive statistics. Results from the hyperpigmentation assessment will be summarized by visit descriptively, including the number of patients that experienced a hyperpigmentation or skin change event. The skin examination listing will show the date of examination, indicator examination was not done (if applicable), reason examination was not done, skin region, result of exam, and any noted findings. A listing displaying the details of skin hyperpigmentation, changes in skin tone, development of new moles, changes in existing moles, and AE relatedness will be created.

## 10.8 Bone Age

Bone age will be collected at the enrollment visit (baseline) and the EOT visit. Bone age and the change from baseline to EOT will be summarized using descriptive statistics.

A listing of the date of x-ray, date of bone age assessment, and the result, and the change from baseline will be provided.

# 11 Statistical/Analytical Issues

## 11.1 Handling of Missing Data

In general, the number of patients with missing values will be summarized and reported as appropriate in all outputs. Unless otherwise specified in the SAP, missing data will not be imputed.

## 11.2 Handling of Missing/Partial Dates

While every effort will be made to obtain full, complete information on all data collected the table below outlines the imputation rules to be followed for any missing dates. Dates will be presented as collected in the listings.

### Imputation Criteria for Missing/Partial Dates

Variable	Missing Day	Missing Month or Day and Month	Missing Year, Month and Year, or Day and Year	Missing Day, Month, Year
----------	-------------	--------------------------------	---	--------------------------

AE/Medication Start Date	Assign to the first of the month (i.e. UNK-JAN-2019 becomes 01-JAN-2019)	Assign to the month of 'June' (i.e. 01-UNK-2019 becomes 01-JUN-2019), provided the imputed date is on or after the patient's baseline study treatment date; otherwise, the subsequent month after study treatment will be used.	Assign to year of study treatment will be used (i.e. 01-JAN-UNK becomes 01-JAN-2019), provided the imputed date is on or after the patient's study treatment date; otherwise, the subsequent year after treatment will be used.	Assign to baseline study treatment date
AE/Medication End Date	Assign the last day of the month (i.e. UNK-JAN-2019 becomes 31-JAN-2019).	Assign to the subsequent month after the start date.	Assign to the year of baseline study treatment (i.e. 01-JAN-UNK becomes 01-JAN-2019), provided the imputed date is after the start date; otherwise, the subsequent year after start date will be used.	Assumed medication is ongoing; no imputation

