### 3.2 Overall Design

This is a Phase 3 multi-center, open-label study of setmelanotide in pediatric patients aged 2 to <6 years of age with rare genetic causes of obesity. The study is designed to evaluate safety and tolerability of setmelanotide as well as its efficacy on weight-related parameters in pediatric patients.

The Screening Period begins with obtaining informed consent from the parent or guardian and will last between 1 and 8 weeks. During the Screening Period, patients will undergo all procedures as outlined in the Schedule of Activities (SoA; [Section 16.1](#)) to determine if they meet the all of the Inclusion (Section 6.1 of the protocol) and none of the Exclusion criteria (Section 6.2 of the protocol) for study eligibility.

During the Screening Period, patients will undergo medical evaluation; and caregivers will receive training on injection of study medication and other study procedures.

At the enrollment visit (Day 1), the patient will have height and body weight recorded. This will be the baseline height and weight. To be eligible for the study, a patient's baseline weight must be at least 15 kg. Height and weight will be monitored closely during the study.

During the enrollment visit, the caregiver will inject the patient's first dose of setmelanotide via subcutaneous (SC) injection under the supervision of the study staff. Patients' caregivers will be issued an electronic diary to capture daily compliance with injections.

Patients will have study visits approximately every 4 weeks through Week 20 and then approximately every 8 weeks through Week 52 and assessments will be performed as per the SoA. Due to the young age of the patients, it may not be possible to perform all planned assessments at each visit. Thus, as described in the SoA, the Investigator will be given latitude to adjust the planned assessments and blood draws as appropriate for the optimal medical care of their patients.

The End of Treatment (EOT) visit will occur on Study Day 365, which is the final day of treatment with setmelanotide. A final End of Study (EOS) visit will occur on Study Day 393 and will be conducted via telephone. Patients may be eligible to enroll into a long-term extension study.

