### **10.3 Adverse Events**

An AE is any untoward medical occurrence in a patient or clinical study patient, temporally associated with the use of study treatment, whether or not considered related to the study treatment. An AE can therefore be any unfavorable and unintended sign (including an abnormal laboratory finding), symptom, or disease (new or exacerbated) temporally associated with the use of study treatment. AEs, including Serious Adverse Events (SAE), will be collected from the provision of informed consent until the EOS visit. All AEs reported will be coded using the MedDRA version in force at the time of database freeze) and classified by MedDRA SOC and PT. The MedDRA version used for the coding will be noted as a footnote in the tables and listings.

All AEs will be presented by patient in a data listing. The listing will show the verbatim term, MedDRA SOC, MedDRA PT, event start date, event end date (or ongoing), SAE indicator, severity, relationship to study drug, action taken with study drug, action taken, and outcome.

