#### **10.3.2 Treatment-Emergent Adverse Events**

A TEAE is any AE that begins or worsens in intensity on or after the date of the first administration of study drug. Summaries of TEAEs (including number and percentage of patients) will be displayed by the following:

- TEAEs by MedDRA SOC and PT
- TEAEs related to study drug by MedDRA SOC and PT

- TEAEs leading to drug discontinuation by MedDRA SOC and PT
- TEAEs leading to study discontinuation by MedDRA SOC and PT
- Serious TEAEs by MedDRA SOC and PT
- Serious TEAEs related to study drug by MedDRA SOC and PT
- AEs resulting in death on study by MedDRA SOC and PT

The number and percentage of patients who experienced at least one of the events listed above will be summarized overall and for each SOC and each PT. SOC and PTs will be presented in descending frequency first and then alphabetically if there are ties. Each patient will contribute at most one count per summarization category. In other words, if a patient has more than one TEAE with same PT, the patient will be counted only once for that PT. Similarly, if a patient has more than one TEAE for a SOC, the patient will be counted only once in that SOC and PT.

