### **10.3.4 Relationship to Study Drug**

TEAEs will also be summarized by relationship to study drug and will follow the same methods specified in [Section 10.3.2](#). The relationship of the TEAE is classified into two categories of Related and Not Related. If the relationship assessment is missing, the relationship will be considered related. Related TEAEs will also be summarized by MedDRA SOC, PT and maximum severity (defined in [Section 10.3.3](#)). If the patient experiences both a related and not related TEAE within a particular SOC or PT, only the related TEAE will be summarized in the table.

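### An AE start date with only the day missing is set to the 1st of the month with no first-dose check, so new-onset AEs in the month of first dose drop out of the TEAE tables

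*SAP*

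**What the plan says.** The table of imputation criteria in SAP 11.2 has one row for AE and medication start dates. Its four cells treat first dose differently:

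| What is missing | Imputed start date | Can it fall before first dose? |
|---|---|---|
| Day only | "Assign to the first of the month (i.e. UNK-JAN-2019 becomes 01-JAN-2019") | Yes, no condition is attached |
| Month, or day and month | June of the recorded year if that is on or after treatment; "otherwise, the subsequent month after study treatment will be used" | No |
| Year (alone or with day or month) | Year of treatment if that is on or after treatment, otherwise the following year | No |
| Everything | "Assign to baseline study treatment date" | No |

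SAP 10.3.2 then classifies: "A TEAE is any AE that begins or worsens in intensity on or after the date of the first administration of study drug". SAP 11.2 also says that listings show dates as collected, so the evident use of an imputed AE date is classification for the tables.

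**The concern.** The day-missing cell is the only one that can move an AE from after first dose to before it. The more that is known about the date, the worse the result: an AE with no date becomes a TEAE, while a new-onset AE known to lie in the month of first dose does not. This conflicts with the protocol's own definition (section 8.6.1.1), which counts any event not present before exposure.

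The error is anti-conservative. Elsewhere the SAP resolves missing safety data the other way: missing severity is counted as severe (SAP 10.3.3), and "If the relationship assessment is missing, the relationship will be considered related" (SAP 10.3.4).

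Frequency and severity of AEs is a secondary endpoint. Apart from the death rows, the AE incidence, severity and relationship tables in SAP 10.3.1 to 10.3.5 are TEAE tables. The loss falls mainly on the first days to weeks of treatment, at the starting dose.

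**Working it through.** The plan gives no figure to reproduce, so the check applies the two rules to dates.

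**Example.** First dose 15 March, AE start UNK-MAR of the same year. The imputed start is 1 March, 14 days before dosing, so the AE is not a TEAE unless it is recorded as worsening after first dose.

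**When an AE is lost.** A day-missing, new-onset AE is lost exactly when its onset is in the calendar month of first dose and first dose was not on the 1st. In any later month, the 1st is already after first dose and nothing is lost.

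**Assumptions.** First-dose dates uniform over a 365-day year, onset uniform over the window, and missing day unrelated to onset date.

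**Count.** Let d be days since first dose (d = 0 is Day 1). In a month of L days, L − 1 − d first-dose dates lead to loss, when that is positive. Summed over 12 months:

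- d = 0 to 27: 365 − 12 − 12d = 353 − 12d
- d = 28: 7 × 2 + 4 × 1 = 18 (seven 31-day and four 30-day months)
- d = 29: 7 × 1 = 7
- d ≥ 30: 0

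**Share lost** = sum of these counts over the window ÷ (365 × days in window):

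| Study days | Calculation | Lost |
|---|---|---|
| 1-7 | (7 × 353 − 12 × 21) / 2,555 = 2,219 / 2,555 | 86.8% |
| 1-14 | (14 × 353 − 12 × 91) / 5,110 = 3,850 / 5,110 | 75.3% |
| 1-28 | (28 × 353 − 12 × 378) / 10,220 = 5,348 / 10,220 | 52.3% |
| 1-30 | (5,348 + 18 + 7) / 10,950 = 5,373 / 10,950 | 49.1% |
| 1-56 | 5,373 / 20,440 | 26.3% |
| 1-365 | 5,373 / 133,225 | 4.0% |

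Restricting first-dose dates to February to September 2022, which the protocol's estimated study dates suggest, gives 75.2% (days 1-14), 48.8% (days 1-30) and 4.0% (days 1-365).

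**Where the exposure lies.** The exposed period averages 5,373 / 365 = 14.7 days per patient. Of it, 3,850 / 5,373 = 71.7% is study days 1-14, before the Day 15 escalation visit. A further 1,498 / 5,373 = 27.9% is days 15-28, and 25 / 5,373 = 0.5% is later. In a 31-day month, a patient first dosed on the 2nd is exposed on days 1-30, on the 15th on days 1-17, on the 28th on days 1-4, and on the 1st on none.

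**Trial scale.** With the planned 10 to 15 patients, one reclassified patient moves an incidence by 1/15 = 6.7 to 1/10 = 10 percentage points, provided that patient has no other event in the same row.

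**The case against.** The strongest counter-argument is that the effect may be nil. Protocol 8.6.4 requires onset date and time, SAP 11.2 promises every effort to obtain complete dates, and AEs are reviewed at Screening, Day 1 and the escalation visits. Recall is therefore only about two weeks over most of the exposed period. The percentages above are conditional on a missing day, and nobody knows how often that will occur. This stands, and it limits the weight of the point.

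Other limits also stand:

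- The AE remains in the all-AE listing, and the SAE and discontinuation listings are not confined to TEAEs.
- Injection-site findings (SAP 10.2.3) and skin changes (SAP 10.7) are also summarised by visit without a TEAE flag, although that does not put the AE back into the TEAE tables.
- The interim analysis in SAP section 12 does not list AE tables.
- A supplemental cohort would shrink the effect of one patient.
- The separate programming conventions (SAP section 14) and the redacted part of SAP section 4 could not be read, and either might contain a repair.

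None of this makes the written rule right. It exists for incomplete dates, and when one occurs in the month of first dose it classifies wrongly for every patient not first dosed on the 1st.

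**Conclusion.** The concern holds. Read with SAP 10.3.2, the day-missing rule removes new-onset AEs in the month of first dose from the TEAE tables, and no readable text corrects it. The mechanism follows from the text alone. The sizes (75% of day-missing, new-onset AEs from days 1-14, 4% over the year) rest on the uniformity assumptions stated above.

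AEs with complete dates, day-missing AEs in later months, AEs recorded as worsening after first dose, and patients first dosed on the 1st are unaffected. The SAP should be corrected, but the point does not threaten the trial's conclusions on its own: the number of affected AEs may be zero and no hypothesis test depends on it.

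**What to change.** Split the shared AE/medication start-date row, leave the medication rule as it is, and state for AE start dates:

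> If only the day is missing and the month and year equal those of first dose, impute the first-dose date, unless the AE end date as collected (not imputed) shows that the AE ended before first dose. Otherwise impute the 1st of the month.

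The words *as collected* are needed because the end-date row says "Assign the last day of the month (i.e. UNK-JAN-2019 becomes 31-JAN-2019"), and the last day of the first-dose month is never before first dose. In practice only a complete end date can meet the exception. If the eCRF holds other evidence of pre-dose onset, such as an AE already entered at Screening, the exception could be widened to include it.

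The work is one added condition in the SAP table and the program. The share lost falls to 0% in every window.

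The statistical cost is an error in the conservative direction. Screening AEs are in the database ("AEs, including Serious Adverse Events (SAE), will be collected from the provision of informed consent until the EOS visit"), and SAP 3.2 allows 1 to 8 weeks of screening. Onset k days before dosing falls in the first-dose month for 365 − 12k of 365 dates (k up to 28), so for a 1-week screening period (7 × 365 − 12 × 28) / 2,555 = 2,219 / 2,555 = 86.8% of day-missing screening AEs would count as TEAEs, against 0% now. The corresponding figures are 75.3% for 2 weeks, 52.3% for 4 weeks and 26.3% for 8 weeks, equal to the shares lost today over windows of the same length.

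A complete end date reduces this. An assumed 3-day AE is kept only if it began 1 or 2 days before dosing: (353 + 341) / 2,555 = 27.2% for 1 week of screening, falling to 694 / 20,440 = 3.4% for 8 weeks. For an assumed 7-day AE (onset 1 to 6 days before dosing) the figures are 1,938 / 2,555 = 75.9% and 1,938 / 20,440 = 9.5%. Without a complete end date there is no reduction. Counting doubtful events is the direction the SAP already takes for missing severity and relationship.
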